Aim 3: Determine the influence of a menthol flavor ban on tobacco purchasing behavior in the context of a reduced nicotine standard using an ETM. At Visit 5, participants will complete two ETMs in the laboratory to model the impact of menthol flavoring and nicotine content on cigarette purchasing in the context of all available tobacco products currently on the market. ETM 1 will evaluate willingness to purchase and smoke non-menthol VLNCs at increasing prices under the scenarios where a

nicotine reduction policy is in effect and menthol is banned in combustible cigarettes. ETM 2 will evaluate willingness to purchase and smoke menthol vs non-menthol VLNCs at increasing prices under the scenario where a nicotine reduction policy is in effect but menthol in combustible cigarettes is available. In both ETMs, all ATPs will be available in different flavors, including menthol, to simulate the real-world marketplace. Hypothesis: In ETM 1, YAs will be more likely to choose an ATP than purchase any cigarettes. In ETM 2, YAs will be more likely to purchase menthol VLNCs or ATPs than purchase non-menthol VLNCs or no tobacco products.

Exploratory Aim: Determine the influence of a menthol flavor ban on tobacco purchase behavior when menthol is banned in all combustible tobacco products (cigarettes, cigars), but is available in non-combustible products (e.g., e-cigarettes).

The proposed research design is unlike existing research, as it combines rigorous, controlled laboratory paradigms of smoking response with “real-world” measurements of the same to determine the relative impact of menthol characteristics and nicotine on cigarette smoking in YAs, a vulnerable group of tobacco users, and adults aged 26-34, who also have high rates of menthol cigarette use. Beyond informing policy, this proposal will validate a new set of measures to be used in future studies to evaluate the potential impact of tobacco policies (e.g., a ban on all flavors) on YA cigarette and alternative tobacco use behavior.

B. Background and Significance

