C.6. Laboratory Visit 5 (V5) and ETM Procedure. Participants will complete the ATSQ, mFTQ, MNWS, and QSU after which two separate ETM³⁻⁶ tasks (counterbalanced) will be administered at the conclusion of the laboratory and take home trials (V5) to >12 hour abstinent participants. In the tasks, participants will be shown an online virtual ‘marketplace’ of cigarettes and all combustible and non-combustible tobacco products that are available on the market. Participants will be instructed to complete the task as if they were purchasing the products from a retailer, and told to make purchases of cigarettes and/or alternative tobacco products that they would take home and use for the week. The price of cigarettes will increase over eight trials (\$0.12, \$0.25, \$0.50, \$1.00, \$2.00, \$4.00, \$8.00, and \$16.00 per cigarette). The prices of alternative products available on the market will remain fixed, and will reflect the average cost of these products in Oklahoma. The first iteration of the task (ETM 1) will assess participant’s willingness to purchase non-menthol VLNCs at increasing prices, where no other types of cigarettes will be available (e.g., menthol NNCs; menthol VLNCs); this will model a scenario where a nicotine reduction policy is in effect and menthol in combustible cigarettes is banned. Findings from ETM 1 will inform FDA whether the presence of menthol-containing tobacco products, beyond cigarettes, leads to significant changes in combustible and non-combustible product use. The second iteration of the task (ETM 2) will assess participant’s willingness to purchase menthol VLNCs at increasing prices, where non-menthol VLNCs are available but no other cigarette types (e.g., NNCs) are available; this will model a nicotine reduction policy without a menthol ban. The prices for non-menthol VLNCs in ETM 1 and menthol VLNCs in ETM 2 will be presented at increasing prices. All alternative tobacco products presented in the ETMs will be available in different flavors, including menthol, to simulate the real-world marketplace.

Participants will receive account balances approximately equal to the money they spend on tobacco in one week. They will be instructed that they can ‘save’ unspent money, and purchase as many or few tobacco products as their account balance allows, including no tobacco products at all. Results of the ETM will not be actualized – meaning the ETM will be hypothetical and they will not receive

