Primary Outcomes: (a) The relative reinforcing value (RRV) of usual brand cigarettes vs menthol VLNCs; (b) RRV of non-menthol VLNCs vs menthol VLNCs. RRV will be operationalized as within-subject differences in subjective ratings of cigarette appeal/reinforcement (satisfaction, reward, craving reduction, physical sensations) during each ad libitum smoking session. Secondary Outcomes: (a) CO boost; and (b) puff topography (number of menthol versus non-menthol cigarette puffs consumed, number of minutes smoked, interval between puffs).

Analysis of covariance will be conducted to examine effects of cigarette type (usual brand, menthol VLNC, non-menthol VLNC) on the outcomes of interest, controlling for cigarettes per day (CPD), nicotine dependence, race/ethnicity, gender, and age of smoking onset as potential covariates. Factors related to study drop-out and differences in cigarette compliance will also be examined as potential covariates. Exploratory analyses will examine differential reactions to usual brand and each research cigarette by race/ethnicity (White, Black, Hispanic, Other) and by gender. Significant interactions will be followed up with individual contrasts of cell means using Fisher's Least Significant Difference tests. We will examine whether topography differs as a function of in-person versus remote session.

3. EMA Analyses (Aim 2)

Primary Outcomes: (a) within-day subjective response (craving reduction, satisfaction, psychological reward, physical sensations like throat grab) to the most recent cigarette smoked; (b) within-day number of research cigarettes smoked per day; (c) within-day number of non-research cigarettes smoked; and (d) within-day withdrawal intensity. Secondary Outcomes: (a) within-day use of alternative tobacco products; (b) changes over the course of days (creating an average change score for each person) for each outcome; (c) number of days abstinent from tobacco use.

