Patterns of missing data, compliance, distributional properties of variables, and correlations among all measures will be assessed. We will control for potential variables related to missing data and utilize multiple imputation methods (expectation maximization algorithm).¹⁶⁰⁻¹⁶³ Analysis will use linear mixed modeling with random subjects effects^{164,165} to assess the main effect of cigarette type on the primary and secondary outcomes of interest. Models will use a contrast to compare differences between menthol VLNC and non-menthol VLNC at the day-level on predictions of the outcome of interest and that outcome of interest at time t (e.g., morning) predicting behavior (number of cigarettes, any smoking, craving, withdrawal) occurring at a subsequent time point (controlling for cigarette consumption from the previous report). Comparison of usual brand and the menthol VLNC ratings will also be made to determine the perceived similarity of the VLNC to one's own brand. A sub-group of respondents may have fixed (unchanging) ratings of subjective response, craving, cigarettes per day, or withdrawal over the course of 7 days, although this is unlikely given the team's previous research. We will examine baseline and daily factors that set "no changers" apart from those whose show fluctuations in these factors, and examine these as potential covariates in models. Within-person slopes capturing associations between cigarette type and the EMA outcome of interest will be saved in regression models and used to predict the ETM responses.

4. ETM Analyses (Aim 3)

Primary Outcomes: (a) consumption of alternative tobacco products (milligrams of nicotine for alternative tobacco sources) as a function of cigarette type available. Typically, as cigarette price increases, consumption of other tobacco products increases.¹⁴ Secondary Outcomes: (a) breakpoint: the first price at which consumption of the available cigarette is zero; (b) intensity of demand: consumption at the lowest price); (c) elasticity of demand: sensitivity of cigarette consumption to increases in cost, (d) Omax: maximum expenditure for cigarette type available; and (e) Pmax: price at which expenditure is maximized.

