The analyses for the aim using ETM data will examine the predictive validity of laboratory and EMA data on the ETM outcomes of interest, separately for each cigarette type. Hierarchical linear regression models will predict the ETM outcome of interest, controlling for baseline cigarettes per day, nicotine dependence, other tobacco use, and relevant demographics in Step 1 and then

including the laboratory or EMA-derived slopes of appeal/reinforcement in Step 2. Models will separately examine the effects of laboratory and EMA measurements of appeal/reinforcement on the ETM outcomes of interest.

5. Exploratory Analyses

Differences by age (18-24 vs 25-34), sex, race/ethnicity, alternative tobacco product use, and ETM flavor and product preference. Menthol cigarettes are disproportionately used by women, as well as Black and Hispanic smokers.^{18,166-168} As such, sex and race/ethnicity will be examined as moderators of outcomes, as sample size permits. This allows us to adhere to NIH guidance examining sex as a biological variable. Variation in the use of alternative tobacco products during each 7-day take-home phase will be examined as a possible moderator of the reinforcing effects of the research cigarette to which participants are assigned, as well as an outcome assessment of compensatory tobacco use. Given the popularity of menthol cigarette use in adults aged 26-34 years and alternative tobacco product use in this age group,^{17,169-171} flavor preference by product type (e-cigarettes, little cigars) will be examined as an exploratory outcome from the ETM analyses.

Laboratory and EMA concordance and predictive utility. We will examine the association of laboratory and EMA measurements of appeal/reinforcement and determine whether correlations between these measures differ in magnitude by menthol vs non-menthol use and by VLNC vs usual brand. A weak or non-significant correlation could indicate that these paradigms tap into different dimensions of reinforcement/appeal. We will also compare the utility of laboratory vs EMA outcomes as predictors of ETM outcomes to determine the relative contribution of each measurement paradigm. This would advance theoretical models and facilitate future research by identifying the most relevant aspects of abuse liability that uniquely account for the role of menthol in increasing risk for dependence.

6. Study Timeline.

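### Section J.4 states no test of the menthol-ban effect and none of the two Aim 3 choice hypotheses; its only stated analysis is predictive regression

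*Combined protocol and SAP*

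**What the plan says.** Section A gives Aim 3 as: "Determine the influence of a menthol flavor ban on tobacco purchasing behavior in the context of a reduced nicotine standard using an ETM". It attaches one directional hypothesis to each task. For the ban scenario: "In ETM 1, YAs will be more likely to choose an ATP than purchase any cigarettes". For the no-ban scenario: "In ETM 2, YAs will be more likely to purchase menthol VLNCs or ATPs than purchase non-menthol VLNCs or no tobacco products".

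Section C.6 has the same participants complete both tasks at Visit 5 in counterbalanced order, each over eight cigarette prices from $0.12 to $16.00.

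J.4 gives the primary ETM outcome as "consumption of alternative tobacco products (milligrams of nicotine for alternative tobacco sources) as a function of cigarette type available". Breakpoint, intensity, elasticity, Omax and Pmax are secondary. The analysis paragraph then says that the analyses for the aim will "examine the predictive validity of laboratory and EMA data on the ETM outcomes of interest, separately for each cigarette type". The models are two-step regressions: baseline smoking, dependence, other tobacco use and demographics first, then a laboratory or EMA measure of appeal.

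The other two aims are handled differently. For Aim 1, J.2 says: "Analysis of covariance will be conducted to examine effects of cigarette type (usual brand, menthol VLNC, non-menthol VLNC) on the outcomes of interest". For Aim 2, J.3 specifies a linear mixed model "to assess the main effect of cigarette type on the primary and secondary outcomes of interest", with a menthol versus non-menthol contrast.

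J.1 states that the laboratory, EMA and ETM methods are all adequately powered for their primary outcomes.

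**The concern.** The analysis named for Aim 3 answers a different question from the aim. The aim and its primary outcome compare two policy scenarios, and the hypotheses compare choices within each scenario. The regressions ask which participants buy more, given how appealing they found the cigarettes.

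The answer on a menthol ban therefore has no pre-stated estimate, interval or test. If the gap is filled later, the contrast, and the price or summary it uses, may be chosen with the data in view. J.6 places preliminary analyses at months 13-14, inside the data-collection window of months 7-28. The compensation section refers to loss to follow-up already above expectation, so the study appears to be under way.

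**Working it through.** **1. Question and stated analysis, side by side**

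| Aim | Question | Stated analysis | Condition comparison named? |
|---|---|---|---|
| 1 (J.2) | Response by cigarette type | Analysis of covariance | Yes |
| 2 (J.3) | Daily response by cigarette type | Mixed model with contrast | Yes |
| 3 (J.4) | Purchasing with and without a ban; choices within each task | Regression on laboratory or EMA measures, split by cigarette type | No |

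J.5 adds exploratory flavor and product preference, moderators, and a comparison of laboratory with EMA predictors. None of these is a scenario contrast or a test of the section A hypotheses.

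**2. What the regressions estimate.** Let Y_is be alternative-product nicotine for person i in scenario s, X_i the Step 1 covariates and Z_i the appeal measure. Reading the split as one model per scenario:

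- Model: Y_is = a_s + b_s·X_i + c_s·Z_i + error
- Target of the aim: Δ = mean of (Y_i1 − Y_i2)

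The reported quantity is c_s, an association within one scenario. With centred covariates, least squares makes a_s the scenario mean, so a_1 − a_2 equals the mean difference when the same people are in both models. Its precision, before covariate adjustment, is SE² = (s_1² + s_2² − 2·r·s_1·s_2)/n, where r is the within-person correlation. Separate models never estimate r. They can give two means, but no paired standard error, interval or test.

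The split is itself unclear. ETM 2 offers both study cigarettes, so cigarette type is not the same as scenario.

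**3. The choice hypotheses.** Each compares purchase events within a person in one task. A regression of milligrams or a demand index on appeal contains neither comparison. C.6 also allows baskets that mix cigarettes and alternative products, and no rule classifies them.

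**4. The plan's own figure.** J.1 gives power 0.8 at n = 100. It cannot be reproduced for the ETM, because no test, alpha, effect size or SD is stated. For feasibility only, at an assumed two-sided alpha of 0.05, the detectable standardised paired difference is dz ≈ (1.960 + 0.842)/√n:

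- n = 100 (J.1): 2.802/10 = 0.280; noncentral t, 0.283
- n = 138 (C.4, including the supplemental sample; 172 × 0.8 = 137.6): 2.802/11.75 = 0.238; noncentral t, 0.240

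**5. Illustration of choosing a price afterwards.** Suppose there is no ban effect and an analyst reports whichever of the eight paired contrasts reaches p < 0.05 (simulation, n = 100):

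| Assumed correlation between prices | Chance of at least one |
|---|---|
| Equal, 0.5 / 0.7 / 0.9 | 25.1% / 19.2% / 12.1% |
| Decaying along the ladder, adjacent 0.7 / 0.9 | 24.8% / 16.2% |
| 0.99, equal / adjacent | about 7% / about 8% |

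In the first five settings, a pre-stated mean over the eight prices stayed at 4.9% to 5.1%. The documents give no correlations.

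**6. The ETM 2 price of the non-menthol study cigarette.** Section A describes menthol versus non-menthol study cigarettes at increasing prices in ETM 2. Section B has the study cigarettes rise while other products stay fixed. C.6 first says that cigarette prices rise, then names only the menthol study cigarette as rising in ETM 2.

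If the non-menthol price is fixed at P in ETM 2, then at ladder step p it costs p in ETM 1 and P in ETM 2. These agree only where p = P. On at least seven of the eight steps, an ETM 1 minus ETM 2 difference would then mix the ban with a price difference.

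**The case against.** The strongest reply is that the primary outcome is defined by the cigarette type available, so the scenario comparison is implied, and that separate models can still yield scenario means. Part of this stands. A reader might infer that the plan can produce no estimate at all of the ban effect. That goes too far, as step 2 shows. But an outcome definition names no model, price, summary or test, and the analysis paragraph splits the data where a comparison would have to join them.

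The regressions are also deliberate. Section B expects appeal to be linked to ETM purchasing, and C.6 wants ETM results compared with laboratory and EMA patterns. That stands: they belong in the plan, but they do not test the aim.

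It is tempting to cite C.6, where ETM 1 is to show whether something "leads to significant changes in combustible and non-combustible product use", as a promise of the ETM 1 versus ETM 2 test. The subject of that sentence is menthol in products beyond cigarettes, so it does not support that reading.

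A reader might also infer that the false-positive rate will reach 25%, or that the contrast is bound to be chosen after seeing data. The documents support neither. No section proposes picking a single price. J.6 does not say whether the month 13-14 analyses include ETM data, and it plans a protocol manuscript at the end of Year 1 whose content is not given.

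Finally, both hypotheses are choices within one task, so making the between-task contrast primary is a judgement. It rests on the wording of the aim and the J.4 outcome.

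**Conclusion.** The point holds on the text. J.4 names a primary ETM outcome and section A states two hypotheses, but the plan attaches a paired contrast, interval or test to none of them. This is more than brevity: the analysis stated for the aim has a different target, and J.2 and J.3 show that condition comparisons were named where intended. It should be corrected before any further ETM analysis.

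The gap has no single numerical size. The detectable differences of 0.28 and 0.24 show only that a paired test is feasible, given the assumed alpha and power. The 12% to 25% range illustrates one way in which an open choice could go wrong, under assumed correlations of 0.5 to 0.9. Data-driven selection is a risk, not an established consequence.

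One part of the preliminary-studies section was not available; it is an unlikely place for an ETM analysis.

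**What to change.** 1. **Settle the price first.** Reconcile sections A, B and C.6 on whether the non-menthol study cigarette rises in price or stays fixed in ETM 2. The primary summary depends on the answer.
2. **Name the primary Aim 3 test** before any (further) ETM analysis: a within-person ETM 1 minus ETM 2 contrast of alternative-product nicotine (mg), allowing for task order. One way is to regress the difference on order coded −1/+1 and test the intercept. If non-menthol prices match across the tasks, use one pre-stated summary over the eight prices. If the ETM 2 price is fixed, use the ladder step where prices match, if there is one, or state that the contrast mixes ban and price effects.
3. **Test the two section A hypotheses** with within-person comparisons at a pre-stated price or summary, and keep no purchase as its own category. Give a mixed-basket rule that does not move with cigarette price, for example by nicotine or units. Share of spend would not do: the cigarette price varies by a factor of 16.00/0.12 = 133 along the ladder, so an identical basket could change class. A nicotine rule will lean toward alternative products, since the study cigarettes hold 0.4 mg/g, so give the reason for the choice.
4. **Keep the hierarchical regressions as secondary**, and disclose with the amendment any ETM analysis already done.

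The cost is SAP wording and a little extra analysis. No new data are needed, since each participant is to complete both tasks at Visit 5. The downside is that the regressions lose their place as the lead analysis.

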At the end of V2, participants will receive the first set of assigned research cigarettes and will be asked to smoke those cigarettes in their home environment for 7 days; starting on the day after V2. The ordering of flavor of the research VLNCs to be smoked (menthol and non-menthol) will be counterbalanced and assigned prior to Visit 2 (Individuals who complete the session remotely will be scheduled for a pick-up date to get the VLNCs1). During each 7-day period of exposure, participants will be instructed to switch their usual brand cigarette for the assigned research cigarette and will provide daily data on smoking quantity, craving, withdrawal, subjective response, and alternative tobacco product use via twice daily EMA surveys. We will allow for other tobacco product use without specific instruction to align with the real-world scenario, as these products will exist on the market even if a menthol ban and/or a reduced nicotine standard are enacted. Given the high prevalence of dual and poly-tobacco use in this age group, we will examine change in alternative tobacco product use between conditions as a secondary outcome in exploratory analyses, per Co-I [name]'s and [name]'s previous work. Participants will have a 7-day period wash-out period of return to smoking as usual (own brand of cigarette) between the experimental conditions.

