Smoking during pregnancy can lead to miscarriage, preterm delivery, stillbirth, birth defects, and other problems. To avoid risks to the participant and fetus, female participants will be tested for pregnancy at every smoking visit or session. If a participant becomes pregnant during the study, she will be withdrawn from the study.

A Randomization and Product Tracking database will be used in REDCap (the electronic data capture system) to track participants’ use of menthol and non-menthol study cigarettes. Randomization of when participants will smoke the menthol and non-menthol study cigarette will be deployed and tracked within REDCap, and presented by the Project Manager in a weekly CONSORT diagram presented at weekly project team meetings.

Process of Adverse Event (AE)/Serious Adverse Event (SAE) collection.

While participating in the trial, adverse events, serious adverse events, and changes in medications will be assessed at every study visit and carbon monoxide will be obtained. Medical events will typically be identified during the administration of the **Adverse Events Form** and the Health Changes Questionnaire. Other events may be identified by spontaneous reports during non-scheduled assessments. Participants will also be given an emergency number they can call if necessary.

No new AE is considered if one or more conditions below are met and the description does not otherwise meet the definition of an AE.

- 1) Existing AE already open for reported symptom.
- 2) Pre-existing condition without increase in severity or frequency of symptoms (brief medical history will be updated if not previously reported).
- 3) Received preventative or follow-up medical care.
- 4) Other (as determined by the PI and medical monitor).

Serious adverse events (SAEs): Information about all serious adverse events will be collected and recorded on a standard Serious Adverse Event Report Form. To ensure participant safety, each study-related serious adverse event will also be reported to the IRB office within 24 hours and NIDA Program Officer within 72 hours of learning of its occurrence. A serious adverse event is an undesirable sign, symptom or medical condition which:

1. is fatal or life-threatening
2. requires or prolongs hospitalization
3. results in persistent or significant disability/incapacity
4. constitutes a congenital anomaly or a birth defect

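### The Aim 3 regressions leave out the randomised VLNC order, so a change between the two VLNC weeks stays in each person's slope and can weaken or bias its association with ETM purchasing

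*Combined protocol and SAP*

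**What the plan says.** J.4 (ETM Analyses, Aim 3) specifies hierarchical linear regressions of the ETM outcomes, "controlling for baseline cigarettes per day, nicotine dependence, other tobacco use, and relevant demographics in Step 1". The second step adds the person's appeal slope, taken from the laboratory sessions or from EMA. The regressions are run separately for each cigarette type and separately for laboratory and EMA measures.

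The EMA slopes come from J.3. That section uses a linear mixed model with random subject effects "to assess the main effect of cigarette type on the primary and secondary outcomes of interest"; the within-person cigarette-type slopes "will be saved in regression models and used to predict the ETM responses". The laboratory model in J.2 adjusts for person-level covariates. Neither section names a period, sequence or order term.

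The order itself is part of the design. Under Smoking Session 1 (V2): "The ordering of flavor of the research VLNCs to be smoked (menthol and non-menthol) will be counterbalanced". Section K adds: "Randomization of when participants will smoke the menthol and non-menthol study cigarette will be deployed and tracked within REDCap". Section C.6 places ETM 1 and ETM 2 at V5, after both VLNC weeks, with the order of the two tasks also counterbalanced.

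**The concern.** Counterbalancing cancels a shared week-to-week change from the mean menthol contrast. It does not cancel it from an individual's slope, because each person smokes each VLNC in one week only. Aim 3 is a between-person regression on those slopes, so the protection that holds for the mean comparison does not carry over.

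This regression is the only analysis J.4 describes for Aim 3. A period change left in the slope makes a real link between appeal and purchasing harder to see. If order also affects purchasing, it becomes a common cause of predictor and outcome, and the estimated link may be too large or too small. A period change is plausible: participants are not blinded to nicotine content (Research Design, item 4), they may adapt to VLNCs, and the protocol itself measures reactivity to EMA.

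**Working it through.** **The plan's own figure.** Section J.1 states power of 0.8 at n = 100. It gives no effect size, SD, alpha or test, and nothing specific to Aim 3, so it cannot be reproduced. Taking two-sided alpha 0.05 as an assumption, the correlation detectable with 80% power at n = 100 is tanh[(1.960 + 0.842)/√97] = 0.277. A true correlation of 0.28 is therefore used below. Section C.4 expects 138 analysed with the supplement, so n = 138 is shown as well.

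**How order enters the slope.** Let ratings shift by d from the first to the second VLNC week for everyone, and let τ be the person's true contrast.
- Slope as menthol minus non-menthol VLNC: τ − d if menthol comes first, τ + d if second. The orders differ by 2d.
- Slope as one VLNC against usual brand: usual brand always comes first, so only the VLNC's own week changes. The orders differ by d.

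The plan does not say which slope is meant. Order enters under both.

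**Formulas.** Let Ds be the between-order difference in mean slope and De the between-order difference in mean ETM outcome, each in within-order SDs. Both are assumptions. Allocation to the two orders is taken as 1:1, since no ratio is stated. With true within-order correlation r, the correlation seen when order is omitted is

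r_obs = (r + Ds·De/4) / √[(1 + Ds²/4)(1 + De²/4)].

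The rejection rate follows from Fisher's z: atanh(r_obs)·√(n − 3) compared with ±1.96.

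**Period effect only (De = 0, r = 0.28, n = 100).**
- Ds = 0: r_obs = 0.280, power 81%.
- Ds = 0.6: 0.28/√1.09 = 0.268, power 77%.
- Ds = 1.0: 0.28/√1.25 = 0.250, power 71%.

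Simulation agrees to within about two points. With order in the model, power returns to about 80%.

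**Period effect and an order effect on purchases.** Simulated figures are from least squares, most of them with four null Step 1 covariates.

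| True r | Ds / De | n | r_obs | Rejection by formula | Simulated, order omitted | Simulated, order included |
|---|---|---|---|---|---|---|
| 0 | 0.2 / 0.2 | 100 | 0.010 | 5.1% | 5.4% | 5.2% |
| 0 | 0.5 / 0.5 | 100 | 0.059 | 8.9% | about 8.6% | about 5% |
| 0 | 0.5 / 0.5 | 138 | 0.059 | 10.5% | about 10.7% | about 5% |
| 0 | 0.8 / 0.8 | 100 | 0.138 | 27.7% | 26.4% | 4.8% |
| 0.28 | 0.5 / 0.5 | 100 | 0.322 | 91% | 90% | 79% |
| 0.28 | 0.5 / −0.5 | 100 | 0.205 | 53% | 52% | 80% |

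For the second row, r_obs = (0.25/√1.0625)² = 0.0625/1.0625 = 0.059. Repeat simulations of the two 0.5/0.5 null rows fall within 8.5–8.7% and 10.4–10.7%. With Ds = 0.5 and De = 0, or the reverse, the simulated false-positive rate stays at about 5% without order.

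**Laboratory-EMA correlations (J.5).** The laboratory and EMA ratings of a given VLNC come from the same period. A shared shift moves both and can raise their correlation; no effect on the ETM is needed.

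**The case against.** The strongest reply is that false positives require two effects, and the documents show neither. By V5 everyone has used both VLNCs, so a change over time common to all participants does not by itself separate purchases by order. A reader might infer that such a change alone could pass as appeal predicting purchasing. It could not: a separate effect on purchases of which VLNC came last is needed, and without it the only harm is loss of power.

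Nor can one say that the assigned VLNC is the last cigarette smoked before V5. Order fixes only the last research cigarette. The risk section lets participants go back to their own brand after each VLNC week, and the text does not state the interval from V4 to V5. All of this stands.

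The design also limits period effects: a usual-brand EMA week and a laboratory smoking session come before any VLNC, and a 7-day wash-out separates the VLNC weeks. This reduces novelty of the procedures but not adaptation specific to VLNCs.

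Two further points stand in part. The Aim 3 hypotheses concern which products are chosen in each scenario, and the slope regression does not test them directly; it is nevertheless the analysis J.4 commits to. And a period term in J.2 and J.3 would remove the shift from the slopes at source, but the plan has none.

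Finally, a reader might treat the order of the two ETM tasks as a second confounder. It cannot influence slopes measured before V5 and, if assigned independently, can at most improve precision.

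**Conclusion.** The omission is real and the mechanism is sound; the size is unknown. A period effect alone weakens the slope-ETM association, costing roughly 4 to 10 points of power at n = 100 for between-order slope differences of 0.6 to 1.0 SD (81 − 77 = 4; 81 − 71 = 10). A false or distorted association also needs an order effect on purchases. At 0.5 SD each the inflation is modest, at 0.2 SD negligible, and it becomes large only when both shifts are near 0.8 SD. The direction can be either way.

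These figures assume two-sided alpha 0.05, 1:1 orders, a true correlation of 0.28 for the power results, and the stated shifts. The documents do not support saying that Aim 3 results will be spurious. They do support closing the gap now, because the remedy costs almost nothing. This is a free improvement.

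**What to change.** In J.4, Step 1, add randomised VLNC order (menthol first or second) as a fixed covariate in every laboratory-slope and EMA-slope model. In J.5, adjust the laboratory-EMA correlations for the two VLNCs for VLNC period. If the slopes are also computed after removing a period effect in J.2 and J.3, keep order in Step 1. ETM task order may be added as an optional precision covariate.

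The cost is one sentence in each of J.4 and J.5 and one degree of freedom, for a factor already tracked in REDCap. When order has no effect, simulated power at n = 100 is 81.0% without it and 80.7% with it.
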